6.1 Accrual and sample size calculations

Recruitment will target enrolling 38 healthy, HIV-uninfected infant participants born by Caesarian section to HIV-infected mothers (HIV exposed, uninfected infants). Although this study is proposed to be a direct comparison with HVTN 115, there are important differences in the populations that justify the inclusion of a larger placebo group. Specifically, we anticipate a higher rate of background severe adverse events in this population, as previous vaccine studies have determined a rate of 18% SAE in the placebo arm (74). This is markedly different from the background rate of severe adverse events in typical HVTN adult studies (~1-2%), supported by emerging safety data from the HVTN 115 study in adults (see Section 4.8.1). Therefore, we propose including a larger placebo group to ensure capacity for determining a safety signal in this vulnerable population.

There are both technical and logistical considerations that favor enrolling infants delivered via Caesarian section. From a technical standpoint, assessment of the evolution of antibodies requires an understanding of the baseline nature of B cells prior to vaccination. Standard assessment of antigen-specific B cell lineages requires several milliliters of blood, a volume that is unsafe in neonates. We intend to protect the participants of the study by performing baseline cellular assays on cord blood that would otherwise be discarded. For logistical reasons related to the study site, cord blood can only be collected during Caesarian sections.

Since enrollment of mother-infant pairs is concurrent with infants receiving the first study vaccination, all participants will be included in the safety analysis. However, for immunogenicity analyses, it is possible that data may be missing for various reasons, such as participants terminating from the study early, problems in shipping specimens, low cell viability of processed peripheral blood mononuclear cells (PBMCs), or high assay background. While the site staff report a historical rate of 10% missingness in infant studies conducted at the site, immunogenicity data from previous phase 1 and 1 phase 2a HVTN trials indicate that 25% is a reasonable estimate for the rate of missing data for the later timepoint (1 year). For this reason, the sample size calculations below account for 25% of enrolled participants having missing data for the primary immunogenicity endpoint.

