Based upon previous HVTN trials as well as experience conducting infant clinical trials in the study population, missing up to 25% of immunogenicity results for a specific assay is anticipated due to study participants terminating from the study early, problems in shipping specimens, or low cell viability of processed peripheral blood mononuclear cells (PBMCs). To achieve unbiased statistical estimation and inferences with standard methods applied in a complete-case manner (only including participants with observed data in the analysis), missing data need to be missing completely at random (MCAR). Following the most commonly used definition, MCAR assumes that the probability of an observation being missing does not depend on any participant characteristics (observed or unobserved). When missing data are minimal (specifically if no more than 20% of participants are missing any values), then standard complete-case methods will be used, because violations of the MCAR assumption will have little impact on the estimates and hypothesis tests.

If a substantial amount of immunogenicity data is missing for an endpoint (at least 1 value missing from more than 20% of participants), then using the methods that require the MCAR assumption may give misleading results. In this situation, analyses of the immunogenicity endpoints at a specific timepoint will be performed using parametric generalized linear models fit by maximum likelihood. These methods provide unbiased estimation and inferences under the parametric modeling assumptions and the assumption that the missing data are missing at random (MAR). MAR assumes that the probability of an observation being missing may depend upon the observed responses and upon observed covariates, but not upon any unobserved factors. Generalized linear models for response rates will use a binomial error distribution and for quantitative endpoints, a normal error distribution. For assessing repeated immunogenicity measurement, linear mixed effects models will be used. If the immunological outcomes are left- and/or right- censored, then the linear mixed effects models of Hughes (80) will be used, because they accommodate the censoring. In addition, secondary analyses of repeated immunogenicity measurements may be done using weighted GEE (81) methods, which are valid under MAR. All the models described above in this paragraph will include as covariates all available baseline predictors of the missing outcomes.

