Based upon previous HVTN trials as well as experience conducting infant clinical trials in the study population, missing up to 25% of immunogenicity results for a specific assay is anticipated due to study participants terminating from the study early, problems in shipping specimens, or low cell viability of processed peripheral blood mononuclear cells (PBMCs). To achieve unbiased statistical estimation and inferences with standard methods applied in a complete-case manner (only including participants with observed data in the analysis), missing data need to be missing completely at random (MCAR). Following the most commonly used definition, MCAR assumes that the probability of an observation being missing does not depend on any participant characteristics (observed or unobserved). When missing data are minimal (specifically if no more than 20% of participants are missing any values), then standard complete-case methods will be used, because violations of the MCAR assumption will have little impact on the estimates and hypothesis tests.

If a substantial amount of immunogenicity data is missing for an endpoint (at least 1 value missing from more than 20% of participants), then using the methods that require the MCAR assumption may give misleading results. In this situation, analyses of the immunogenicity endpoints at a specific timepoint will be performed using parametric generalized linear models fit by maximum likelihood. These methods provide unbiased estimation and inferences under the parametric modeling assumptions and the assumption that the missing data are missing at random (MAR). MAR assumes that the probability of an observation being missing may depend upon the observed responses and upon observed covariates, but not upon any unobserved factors. Generalized linear models for response rates will use a binomial error distribution and for quantitative endpoints, a normal error distribution. For assessing repeated immunogenicity measurement, linear mixed effects models will be used. If the immunological outcomes are left-and/or right- censored, then the linear mixed effects models of Hughes [5] will be used, because they accommodate the censoring. In addition, secondary analyses of repeated immunogenicity measurements may be done using weighted GEE [6] methods, which are valid under MAR. All

the models described above in this paragraph will include as covariates all available baseline predictors of the missing outcomes.

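### The rule for more than 20% missing data moves binary endpoints to a maximum-likelihood binomial model that gives no finite vaccine-placebo odds ratio if no placebo infant responds, and no fallback is named

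*SAP*

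**What the plan says.** SAP 8.4.1 and Protocol 6.4.4.1 carry the same rule.

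- **Expected loss.** The SAP states that "missing up to 25% of immunogenicity results for a specific assay is anticipated". Protocol 6.1 plans on that rate: "the sample size calculations below account for 25% of enrolled participants having missing data for the primary immunogenicity endpoint". The same protocol section also records that "the site staff report a historical rate of 10% missingness in infant studies conducted at the site".
- **Complete-case analysis** is allowed when missingness is minimal, "specifically if no more than 20% of participants are missing any values".
- **Above that limit** ("at least 1 value missing from more than 20% of participants"), "analyses of the immunogenicity endpoints at a specific timepoint will be performed using parametric generalized linear models fit by maximum likelihood".
- **Binary endpoints.** "Generalized linear models for response rates will use a binomial error distribution". No link function is named.
- **Covariates.** "All the models described above in this paragraph will include as covariates all available baseline predictors of the missing outcomes". They are not listed and their number is not capped.

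Earlier in SAP 8.4.1, response rates are compared across groups by Barnard's or Fisher's exact test at a two-sided 0.05, crude rates are given with score intervals, and priority goes to the one-sample comparison with zero. Protocol 6.1.2 chooses the visit two weeks after the fifth vaccination because maternal antibody should by then be undetectable. Table 6-4 takes 8 evaluable placebo and 13 evaluable vaccine infants and includes a 0% placebo row.

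**The concern.** The planning rate for missing data lies above the threshold at which the analysis changes, and the wording of the change is mandatory. The design also expects few or no placebo responders at the primary humoral visit. A binomial model fitted by maximum likelihood to an arm with no responders is separated: the likelihood keeps rising as the treatment coefficient grows, so there is no finite estimate and no usable standard error. The covariates cannot cure this, because data separated by treatment alone stay separated when terms are added. Extra terms can only add further ways to separate.

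The plan says nothing about what to do then. The analyst would have to choose a method after seeing the zero cell, and the vaccine-placebo contrast could lack a usable estimate and interval exactly when placebo is clean.

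**Working it through.** **1. The plan's own figures.** Groups 3+5: 18 × 0.75 = 13.5, stated as 13. Pooled placebo: 10 × 0.75 = 7.5, stated as 8. Wilson score intervals at n = 13 reproduce every row of Table 6-3 (for example 8/13: 35.5% to 82.3%), and 0/4 gives the stated upper limit of 49%.

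**2. Probability of the switch.** 20% of 38 is 7.6, so the rule applies at 8 or more participants with a missing value. With X ~ Binomial(38, m):

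| Missing rate m | P(X ≥ 8 of 38) |
|---|---|
| 25% | 0.77 |
| 20% | 0.50 |
| 15% | 0.20 |
| 10% | 0.03 |

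If the rule were applied to Groups 3+5 alone (20% of 18 is 3.6, so 4 or more), the figures are 0.69 at 25% and 0.10 at 10%.

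**3. Probability of no placebo responder.** (1 − p)^8 for true placebo positivity p: 1.00 at 0%, 0.85 at 2%, 0.66 at 5%, 0.43 at 10% and 0.17 at 20%. The documents give no placebo positivity rate, so p is an assumption and the range is shown. A value near 5% is reasonable for BAMA and ADCP, whose cutoffs start from the 95th percentile of the HVTN 115 baseline, although the added criteria may lower it.

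**4. Both together.** Treating the two events as independent and keeping 8 evaluable placebo infants, at p = 5%: 0.769 × 0.663 = 0.51 at 25% missing, and 0.032 × 0.663 = 0.02 at 10% missing.

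**5. What the model returns.** Logit-link fit to 0/8 placebo versus 8/13 vaccine, by number of iterations:

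| Iterations | Log odds ratio | SE | Wald p |
|---|---|---|---|
| 10 | 12.0 | 70 | 0.86 |
| 25 | 27.0 | 1.3 × 10^5 | 1.00 |
| 100 | 37.0 | 1.9 × 10^7 | 1.00 |

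These values show only where the algorithm stopped; none is an estimate. Fits of 4, 9 and 12 of 13 against 0/8 diverge in the same way. Probit and log links also have no finite treatment coefficient. An identity-link risk difference stays finite (8/13 − 0/8 = 61.5%).

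**6. Methods that remain defined, on the same data.**

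| Vaccine (placebo 0/8) | Fisher p | Likelihood-ratio p | Firth log odds ratio (SE) |
|---|---|---|---|
| 4/13 | 0.13 | 0.036 | 2.09 (1.65) |
| 8/13 | 0.0068 | 0.0011 | 3.27 (1.64) |

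For 8/13, Barnard's p is 0.0056 and the Newcombe interval for the risk difference is 20.0% to 82.3%. At 6/13 Fisher gives 0.046 and the likelihood-ratio test 0.007.

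**7. Is the likelihood-ratio test reliable here?** Sum the null probabilities of all 9 × 14 tables with 8 and 13 infants in which the nominal 5% test rejects. The true size is 6.4%, 8.5%, 7.8% and 7.4% at common response rates of 10%, 20%, 30% and 50% (3.2% at 5%). The test is liberal over most of the range.

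**The case against.** The strongest reply is that the gap is narrow, and much of that stands.

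- **No link and no Wald test is specified.** A reader might infer that the analysis, followed as written, yields no p-value at all. The documents do not support that: a likelihood-ratio test from the same model is defined, and so is an identity-link risk difference. The plan chooses neither, however, and the likelihood-ratio test is liberal at about 21 infants.
- **The prioritised analysis is elsewhere.** The one-sample comparison with zero and the crude rates with score intervals do not depend on the placebo cell. Protocol 6.1.2 itself says that power against placebo is low.
- **Many endpoints are outside it.** The named BAMA primary endpoint is a magnitude, handled by the normal-error model. The B-cell phenotyping cutoff is the 85th percentile of placebo, so at least one of 8 placebo infants is positive if values are untied. The listed nAb comparisons are among vaccine arms, precursor rates use Kaplan-Meier, and PVMA differences use Wilson intervals. The ADCC, BAMA and ADCP table lists give rates by group without naming a placebo test, so the contrast rests on the general sentence in SAP 8.4.1.
- **25% is an upper figure.** A reader might infer that the switch is expected whatever happens. At the site's 10% it is unlikely. Still, the protocol noted that 10% and chose 25% for the one-year visit, so the rule should work at 25%.
- **Covariates.** The text limits them to predictors of the missing outcomes, so it does not call for every baseline variable. It gives neither a list nor a cap.
- **Missing-at-random protection.** Dropping the model in favour of exact tests on observed cases would discard a safeguard that the SAP adopted deliberately. That objection is accepted, and the fix keeps the model.

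**Conclusion.** The point holds, within limits. At the planned 25% missingness the change of model is likely (77%). At a 5% placebo rate, the change and an empty placebo cell occur together about half the time (51%), and the vaccine-placebo log odds ratio then has no finite maximum-likelihood estimate under a logit, probit or log link. The plan offers no fallback. At 10% missingness the joint figure is about 2%.

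The exposure is the vaccine-placebo response-rate contrast, mainly for BAMA, FcR-BAMA, ADCC and ADCP; the last three are named secondary endpoints with response rates. It does not extend to the trial's primary immunogenicity conclusions as a whole.

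The sizes assume that infants are missing independently of one another, that missingness is unrelated to response, and that 8 placebo infants are evaluable. The placebo positivity rate is assumed.

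**What to change.** Amend SAP 8.4.1 before unblinding:

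1. For binary endpoints above the 20% threshold, fit the missing-at-random model by Firth-penalised likelihood with penalised profile-likelihood intervals, and state the link.
2. Replace the open-ended covariate rule with a short list of pre-named baseline covariates.
3. At any level of missingness, report the Barnard or Fisher test and the score intervals already named in the section beside the model result.

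The normal-error models for magnitudes need no change on this account. The cost is a few sentences, slight shrinkage of the estimates, and one extra set of results to report.

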3 OBJECTIVES AND ENDPOINTS

3.1 Primary objectives and endpoints

Primary objective 1:

To evaluate the safety and tolerability of HIV-1 CH505 transmitted/founder virus Env gp120 immunogen (CH505TF gp120) adjuvanted with Glucopyranosyl Lipid A - stable emulsion (GLASE) in healthy HIV-1 exposed uninfected (HEU) infants

Primary endpoint 1:

Local and systemic reactogenicity signs and symptoms, laboratory measures of safety, weight gain, and AEs and SAEs

Primary objective 2:

To determine whether vaccination with CH505TF gp120 adjuvanted with GLA-SE initiates B-cell lineages potentially capable of generating a broadly neutralizing antibody response

Primary endpoints 2:

Magnitude of HIV-1 Env gp120, CD4 binding site and V1V2-specific serum IgG binding antibodies, as assessed by BAMA two weeks after the 5th vaccination

Quantification and phenotypic characterization of peripheral B cells capable of binding HIV-1 Env gp120, the CD4 binding site (including differential binding to the I Δ 371 mutant) and the V1V2 binding site, as assessed by flow cytometry two weeks after the 3rd and 5th vaccinations

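### Above 20% missing data, the SAP's single-timepoint model is not unbiased under the SAP's own definition of MAR for the visit-12 B-cell response rate

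*SAP*

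**What the plan says.** SAP 8.4.1 (General Approach) sets the missing-data rules for immunogenicity; Protocol 6.4.4.1 carries the same text.

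- Expected loss: "missing up to 25% of immunogenicity results for a specific assay is anticipated". Complete-case methods are kept up to 20%.
- Above 20%: "analyses of the immunogenicity endpoints at a specific timepoint will be performed using parametric generalized linear models fit by maximum likelihood". For response rates: "Generalized linear models for response rates will use a binomial error distribution".
- Covariates: "the models described above in this paragraph will include as covariates all available baseline predictors of the missing outcomes".
- Property claimed: "These methods provide unbiased estimation and inferences under the parametric modeling assumptions and the assumption that the missing data are missing at random (MAR".
- Definition used: "MAR assumes that the probability of an observation being missing may depend upon the observed responses and upon observed covariates".
- Other tools in the paragraph: linear mixed models are prescribed for repeated measurements, with a version for censored data. Weighted GEE is an optional secondary analysis.

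The second part of primary endpoint 2 is the B-cell measurement, "as assessed by flow cytometry two weeks after the 3rd and 5th vaccinations" (SAP 3.1), which means visits 8 and 12. SAP 9.5 tabulates a response rate at each of these visits. It calls a response when the cell frequency passes the 85th percentile of pooled placebo recipients at the same visit, makes no call at visit 1, and names no missing-data method of its own.

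**The concern.** The three statements in 8.4.1 do not fit together for a response rate at one visit. A binomial model of the visit-12 call is fitted only to infants who have that call. Its estimate is valid if missingness depends on nothing beyond the covariates in the model, and those are baseline covariates. The SAP's definition of MAR is wider because it includes dependence on responses already observed. For the B-cell endpoint the obvious observed response is visit 8, taken in the same infants and the first visit at which a response is called. Missingness related to visit 8 is therefore MAR as the SAP defines it, yet the prescribed model does not correct for it.

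At stake is the accuracy of the visit-12 response rate and its interval. Protocol 6.1.2 describes preliminary estimation of response rates as a main immunogenicity goal, and this branch is the one meant to protect that estimate when losses are substantial.

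**Working it through.** **Plan's own figures.** 18 infants in pooled Groups 3 and 5, less 25%: 18 x 0.75 = 13.5, taken as 13. Power to see at least one responder at a true rate of 30%: 1 - 0.7^13 = 0.990, which agrees with the stated figure of more than 90%. The score interval for 4/13 is 12.7% to 57.6%, as in Protocol Table 6-3. The documents give no figure for bias from missing data.

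**How likely the branch is.** More than 20% of 38 infants means 8 or more (0.20 x 38 = 7.6). The binomial probability of that depends on the missing rate:

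| Missing rate | P(8 or more of 38) |
|---|---|
| 10% (site history, Protocol 6.1) | 3% |
| 15% | 20% |
| 20% | 50% |
| 25% (upper end anticipated) | 77% |

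**Mechanism.** Let p8 be the visit-8 response rate, a and b the visit-12 response probabilities in visit-8 responders and non-responders, d1 and d0 their probabilities of missing visit 12, and m the total missing.

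- True visit-12 rate: p8·a + (1 - p8)·b
- Limit of a visit-12 model without visit 8: [p8(1 - d1)a + (1 - p8)(1 - d0)b] / (1 - m)

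Assume p8 = 0.40, a = 0.50, b = 0.25, m = 0.25. The true rate is 0.20 + 0.15 = 0.35.

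- Non-responders lost more often (d1 = 0.10, d0 = 0.35): (0.18 + 0.0975)/0.75 = 0.37, an error of +2.0 points.
- Responders lost more often (d1 = 0.40, d0 = 0.15): (0.12 + 0.1275)/0.75 = 0.33, an error of -2.0 points.
- If a = b or d1 = d0, the error is zero.

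A baseline covariate does not remove the error. In a simulated population of 400,000 with one such covariate, the true rate was 32.5%, the baseline-only binomial model gave 36.8%, and adding visit 8 gave 32.5%.

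**Size on a continuous scale.** Assumptions: normal visit-8 and visit-12 values, 25% missing at visit 12, true rate 30%, and odds of missing visit 12 that are 2 or 3 times higher per SD lower visit-8 value. With a fixed response cutoff, the estimated visit-12 rate is:

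| Correlation, visits 8 and 12 | OR 2 | OR 3 |
|---|---|---|
| 0.4 | 32.1% | 33.0% |
| 0.6 | 33.2% | 34.5% |
| 0.8 | 34.2% | 35.8% |

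The error is therefore about +2 to +6 points.

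SAP 9.5 does not use a fixed cutoff; the placebo percentile moves with placebo dropout. With the same mechanism and correlation in placebo:

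- dropout driven by rank within arm: 30.0% to 30.7%;
- dropout driven by the absolute visit-8 value: about 28.7% to 29.5%.

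The error is then roughly -1 to +1 point. It stays positive, at about 31% to 35%, only if visit-8 and visit-12 values are weakly correlated in placebo recipients.

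**The case against.** The other side has several good points, and most of them stand.

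- **Visit 8 is not ignored everywhere.** A reader might infer that the visit-8 data go unused. They do not. Mixed models are mandatory for repeated measurements, so quantitative B-cell frequencies are covered if visits 8 and 12 are fitted jointly. SAP 8.4.1 also requires maximum-likelihood cumulative response probabilities, which use earlier visits. Neither yields the visit-12 response rate: the mixed model is linear, and the cumulative method targets a different quantity. Weighted GEE could yield it but is only optional.
- **Direction and size.** A reader might infer that the rate is overstated whenever poor visit-8 responders leave, by the full fixed-cutoff amount. The placebo-derived cutoff undoes that: the error can shrink to almost nothing or change sign.
- **Likelihood of the branch.** The 77% holds only at the upper end of anticipated loss. At the site's historical 10% it is 3%.
- **Mechanism.** The plan attributes losses to early termination, shipping and cell viability. Assay results are not given to participants, and site staff are blinded. Nothing in the documents says that losses track the visit-8 response.
- **Consequence.** The prioritised one-sample comparison with zero rejects on any single responder, so it is little affected.
- **Conditional versus arm-level rate.** A reader might infer that the SAP will report a covariate-conditional rate or odds ratio. It does not say so, and it promises crude rates with score intervals. What is missing is a statement of how an arm-level rate comes out of the adjusted model.

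None of this makes the single-timepoint model unbiased under the MAR that the SAP defines.

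**Conclusion.** The unbiasedness statement in SAP 8.4.1 is too broad. For the visit-12 B-cell response rate, a binomial model with baseline covariates is valid only if missingness depends on those covariates alone. Missingness related to the visit-8 response falls inside the SAP's definition of MAR and outside what the model can correct, so the rate can be biased either way. This follows from the wording and needs no outside figure.

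The size does need assumptions: the correlations, the odds ratios, the placebo mechanism and a 30% rate taken from the low end of the adult HVTN 115 reference. On those, the error is about +2 to +6 points with a fixed cutoff and about -1 to +1 point if placebo losses behave alike. Either is small beside 12.7% to 57.6% for 4/13. The documents do not support a claim that the primary conclusion is unsafe. The point is worth correcting because the remedy is cheap and the data are already collected.

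**What to change.** In SAP 8.4.1 and 9.5, for the visit-12 B-cell response rate when more than 20% are missing, make a method that uses visit 8 the specified analysis. Either would serve:

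1. the weighted GEE already named, with visit-8 frequency in the missingness model; or
2. multiple imputation of visit-12 frequency from arm, visit-8 frequency and baseline, in vaccine and placebo arms alike. The placebo 85th-percentile cutoff and the response call are then made within each imputed data set.

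Report the arm-level rate for all enrolled infants. State that the mixed model for B-cell frequency fits visits 8 and 12 jointly. For the single-timepoint model, limit the unbiasedness sentence to missingness that depends only on covariates in that model, and note that this qualifies the same sentence in Protocol 6.4.4.1.

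The cost is SAP wording and one changed analysis; no new data are needed. The imputation route needs a distributional assumption on log frequency in small arms, the weighted route a model for missingness fitted to few infants. Neither helps infants who have no visit-8 value.
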